#### **Research Data Collection and Management:**

##### **Data Collection**

All data will be recorded on study-specific case report forms (CRFs). Participants will be given a study identification number that will be reported on all CRFs and source documents. Demographic data, diagnoses, prior interventions, both surgical and cardiac catheterization based intervention will be collected. Imaging reports will be reviewed for evidence of anatomic and specific hemodynamic problems of the circuit prior to recruitment of potential participants, thereby allowing us to exclude those patients. Hemodynamic characteristics and ventricular functional characteristics will be recorded at latest follow-up.

##### **Data Management**

Data management will be handled using CCHMC's standard operation procedures and guidelines. Data will be collected by designated research coordinator(s) and the physicians participating in the study. Data will be maintained in REDCap. Only study personnel will have access to data. Data will be indexed

by a study-specific subject number; the key which links this number to identifying information will be stored in a separate, secure location. All study data will be stored in a secure, confidential database.

### **Data Analysis:**

#### **Study Endpoints**

The primary endpoint is exercise endurance as measured by VO2.

The secondary end points are the following;

- Liver stiffness
- Central venous pressure at rest and with exercise
- Peak VO2
- Venous compliance
- Heart rate
- Systemic blood pressure

#### **Statistical Analyses**

Demographic and clinical characteristics of the patient population will be summarized using means and standard deviations or medians and interquartile ranges for continuous variables and frequencies and percents. for categorical variables.

The exercise endurance VO2 and all other study endpoints will be compared between the first and final visits.

Means and standard deviations will be calculated for exercise endurance at baseline and after one month of treatment. The 95% confidence intervals (CIs) for both the mean change and standard deviations will be calculated to obtain estimates of the population values under sampling variability. These values will provide us with a range of plausible values required to inform a rigorous sample size determination for a larger, confirmatory trial of isosorbide dinitrate on exercise capacity assuming no change under placebo. The mean change in VO2 divided the standard deviation will provide a measure of the standardized effect size. We expect a standardized mean difference of at least 0.2 standard deviation units in favor of the investigational agent would reflect a meaningful effect size to help support an encouraging (versus no effect) decision to proceed with a larger, confirmatory trial. We will also formally test whether the change in VO2 in response to isosorbide dinitrate is non-zero using a one-sample t-test or non-parametric alternative. This testing will be conducted using a one-sided alpha of 0.25 since our primary goal is to assess whether there may be preliminary evidence for efficacy and we are willing to accept greater risk of a type I error at this early stage of investigation.

Safety analyses will be conducted by reporting the counts of adverse events (AEs) and serious adverse events (SAEs). Lab values required to monitor patient safety will be determined by the investigators and DSMB. These values will be monitored and values reported to the DSMB over the course of the trial.

Estimates of preliminary efficacy and variability for secondary outcomes will be conducted using the approach described above for the primary outcome.

### **Sample Size Calculation**

Null hypothesis testing is not directly related to achieving the proposed aims. Rather, our goal is obtain sufficiently precise estimates of the parameters needed to inform the design of a confirmatory trial. Based on our experience with this patient population we expect the mean exercise capacity VO2 at follow-up to be around 25 with a standard deviation of approximately 7. We would like to estimate the mean VO2 with a margin of error of not greater than four. A sample size of  $n = 15$  produces a two-sided 95% confidence interval with a distance from the mean to the limits that is equal to 3.9 when the estimated standard deviation is 7. Thus, we will enroll a total of  $n=15$  patients into this pilot study. A sample size of  $n = 15$  produces a two-sided 95% confidence interval with a width equal to 5.9 for the population standard deviation when the sample standard deviation is 7. Thus, we expect  $n= 15$  participants will allow us to obtain estimates of variability with sufficient precision to inform the design of a future confirmatory trial.

### **Risks and Benefits:**

#### **Potential Benefits:**

Each patient may benefit from increasing exercise tolerance and decreasing central venous pressure for the duration of the study. If this were the case, their cardiologist would be notified at conclusion of the study to discuss longer-term nitrate therapy. In addition the information from the study may benefit Fontan patients in the future.

#### **Potential Risks, Discomforts and Inconveniences:**

Potential risks, discomforts and inconveniences of this study include three office visits, two of which will require time and for the patient to undergo intravenous blood pressure measurement. Two of the visits will also require blood draw with similar risks. IV insertion could result in minimal bleeding, bruising and pain in a small portion of people. Furthermore, they will undergo exercise testing at two of these office visits, which is associated with arrhythmias in some patients and/or discomfort.

The risk associated with the medication, isosorbide dinitrate, are primarily due to hypotension which could lead to mild headaches or potentially severe systemic hypotension. Patients will be informed of this potential complication and instructed to contact the office and seek medical attention immediately for any syncopal or pre-syncopal events. Nitrate headaches are a common effect of ISDM and can often be controlled with aspirin or acetaminophen. Such adverse events are dose-related with a low incidence and occur more commonly in the elderly. They will also be told to have the patient lie down and elevate all four extremities to increase central pooling of blood. In the event of any severe reactions, the medication would be decreased to previously tolerated dose or stopped. Furthermore, this is a primary reason for the 3-5 day follow-up phone call. In Fontan patients, lowering blood pressure could also compromise kidney function which is why a 2 week follow-up visit will be performed to assess for any

significant changes to blood pressure at the discretion of the principal investigator based on patient baseline and normal blood pressure readings.

Patients under 18 having a positive pregnancy test will have the results reported to their parents and/or legal guardian. To mitigate the emotional risk from receiving a positive pregnancy result, study staff will offer chaplain services and/or a referral to counseling services. Lastly, there is a potential loss of confidentiality by participating in the study.

### **Risk/Benefit Analysis**

The proposed study has minimal risks associated with it, which are reasonable in relation to the knowledge that will be gained and used to create interventional programs in this high-risk population.

### **Assessment of Safety:**

#### **Adverse Events**

An AE is any untoward medical occurrence associated with the use of a drug in humans, whether or not considered drug related. An AE can be any unfavorable and unintended sign (e.g., an abnormal laboratory finding), symptom, or disease temporally associated with the use of a drug, without any judgment about causality. An AE can arise from any use of the drug (e.g., off-label use, use in combination with another drug) and from any route of administration, formulation, or dose, including an overdose. Adverse events will be recorded from the time of the first dose of study drug until resolution (or study completion).

Events that are unexpected and considered to be related or possibly related to the study procedures as well as breaches of confidentiality, and protocol violations must be reported to the IRB as soon as possible after discovery of the event. All adverse events will be classified by the PI for relationship (Related, Possibly Related, Unlikely Related, Not Related); severity (Mild, Moderate, or Severe); and expectedness (Expected or Unexpected). Events not meeting the criteria for prompt reporting will be reported to the IRB at the time of continuing review.

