### **Baseline visit (Visit 1)**

- Informed Consent
- Baseline vitals (heart rate, blood pressure, oxygen saturation, height and weight)
- Demographic, medical, and medication review
- Urine pregnancy test for all females
- Blood collection (Basic Metabolic Panel-3ml)
- Insertion of peripheral venous cannula for venous blood pressure during exercise testing and estimate of mean capillary filling pressure
- Maximal cardiopulmonary exercise testing/Ramp protocol (including spirometry)
- Liver ultrasound to assess for liver stiffness
- Medication distribution

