### **Visit 6 (4 weeks after visit 3 [+/-2 days] before discontinuing ISDN)**

- Repeat vitals (heart rate, blood pressure, oxygen saturation, height and weight)
- Urine pregnancy test for all females
- Insertion of venous cannula for venous blood pressure during exercise testing and estimate of mean capillary filling pressure
- Maximal cardiopulmonary exercise testing/Ramp protocol (including spirometry)
- Liver ultrasound to assess for liver stiffness
- Recover medication vial
- Perform drug accountability
- Blood collection (Basic Metabolic Panel-3ml)

Table 1 presents schedule of procedures for this study.

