**Table 1: Patient Timeline**

	Visit 1	Visit 2	Visit 3	Visit 4	Visit 5	Visit 6
	Day 0	Day 3 (+/-1 day)	Day 6 (+/-1 day)	Day 9 (+/-1 day)	Day 12 (+/-1 day)	Day 34 (+/- 3 days)
Procedures:						
Informed consent	X					
Demographics and medical history	X					
Medication review	X					
Vital signs	X					X
Urine Pregnancy Test	X					X
Venous pressure a	X					X
Spirometry b	X					X
Maximal exercise ramp test	X					X
Liver Ultrasound	X					X
Quality of Life Survey	X					X
Medication dispensation	X					
Phone call to adjust medications		X	X	X	X	
Collect medication vial						X
Basic Metabolic Panel	X					X
Adverse event monitoring	X	X	X	X	X	X

a Venous pressure will be measured from before exercise test, every 1 minute during exercise, until 5 minutes after exercise.

b Spirometry will occur prior to maximal exercise testing

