#### *Pharmacologic Interventions*

At the conclusion of the first visit ISDN therapy will begin at a small dose (5 mg three times daily in those targeting 20-30 mg TID, less in patients < 40 kg) and be titrated up to goal three times daily over 2 weeks (see Table 2). The medication will be continued for 4 weeks once the target dose is reached. It is an organic nitrate commonly used to prevent angina and used frequently in heart failure as well. It acts upon vascular smooth muscles to cause vasodilation of the peripheral arteries and veins. It should be taken by mouth three times per day with water. It may be taken with or without food.

Patients not tolerating the medication will be instructed to call the clinic for adjustment of medications. Severe side effects to note include pre-syncope, syncope, and severe headache. The PI will assess the patient over the phone and ask them to come in if necessary. Conversation and any changes of

medications will be documented. Less severe symptoms such as mild lightheadedness or headache should attempt to be tolerated or treated with acetaminophen prior to calling the clinic.

Isosorbide dinitrate's clinically relevant interaction is with phosphodiesterase-5 inhibitors, a common medication in Fontan patients. There is a risk for excessive hypotension and therefore, will be a contraindication to enrollment in the trial. ISDN can also affect kidney function. For this reason, a basic metabolic panel will be taken at the start of the study and 1 week after initiation of ISDN.

Side effects will attempt to be reduced by a step-wise up-titration plan, use of acetaminophen for headache, and recommendation to return to previous dose if necessary which may enhance tolerability. Furthermore, patients will be followed up with by phone call 3-5 days after any change in medication.

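### The Adverse Events section starts recording at the first dose, after the Visit 1 cannulation and maximal exercise test, while Table 1 schedules adverse event monitoring at Visit 1; the two need reconciling

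*Combined protocol and SAP*

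**What the plan says.** All references are to the combined protocol and SAP.

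- **Adverse Events** fixes the recording window: "Adverse events will be recorded from the time of the first dose of study drug until resolution (or study completion").
- **Pharmacologic Interventions** fixes when dosing starts: "At the conclusion of the first visit ISDN therapy will begin at a small dose".
- **Baseline visit (Visit 1)** lists "Insertion of peripheral venous cannula for venous blood pressure during exercise testing and estimate of mean capillary filling pressure" and "Maximal cardiopulmonary exercise testing/Ramp protocol (including spirometry"), both ahead of medication distribution.
- **Visit 6** repeats both procedures, and its heading places the visit "before discontinuing ISDN".
- **Table 1** has a row "Adverse event monitoring" with a mark in every visit column, including Visit 1 on Day 0.
- **Potential Risks, Discomforts and Inconveniences** describes exercise testing as a procedure "which is associated with arrhythmias in some patients and/or discomfort", and names minor bleeding, bruising and pain from the IV.
- **Statistical Analyses** plans the safety analysis as counts of AEs and SAEs. It describes no comparison of events before and on drug.

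**The concern.** The protocol gives two answers to the question of when adverse event collection begins. Under the one stated as a rule, the off-drug exercise test lies outside the window and the on-drug test lies inside it.

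That asymmetry matters more here than in most pilots. The trial is single-arm, and safety is part of the Primary Objective. The Background section raises the worry that reduced preload could lower cardiac output during exercise, and treats it as a key question for the study. The Visit 1 test is the only planned off-drug exposure of the same patients to the same procedure. If its events are not collected, an arrhythmia or pre-syncope at Visit 6 has no recorded event history to be read against. The Relationship section grades causality against the study drug only and has no category for a study procedure.

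There is also a participant-protection side. The AE and SAE definitions both refer to occurrences associated with the use of a drug. A hospitalisation after the Visit 1 exercise test, before any ISDN, does not clearly meet the SAE definition. It therefore does not clearly trigger the enrolment pause in the DSMB section.

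**Working it through.** The plan states no figure for this point, so the main check is to set the sections side by side.

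**1. Order of events on Day 0.** Visit 1 lists consent, cannulation, exercise test and liver ultrasound, then medication distribution. Pharmacologic Interventions starts ISDN when the visit concludes. All Visit 1 procedures therefore precede the first dose.

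**2. Each procedure against the two rules.**

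| Procedure | Drug status | Adverse Events section | Table 1 |
|---|---|---|---|
| Visit 1 cannulation and exercise test | off drug | before the window | monitoring marked |
| Visit 6 cannulation and exercise test | on drug | inside the window | monitoring marked |

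The Table 1 mark at Visit 1 can be read in two ways. If it means the whole visit, it contradicts the Adverse Events section. If it means only the time after the first dose on Day 0, there is no contradiction, but the pre-dose procedures remain uncovered. The text does not say which is meant.

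**3. Number of tests affected.** With 15 patients and two tests each, 15 × 2 = 30 tests are planned. Of these, 15 precede the first dose and 15 are on drug. This assumes that every patient completes both.

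**4. How many events could be involved.** The documents give no exercise-event rate, so the rate p per test is an assumption, shown over a range. The expected number at Visit 1 is 15p. The chance of at least one is 1 − (1 − p)^15, taking patients as independent.

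| Assumed p | Expected events, 15p | Chance of at least one |
|---|---|---|
| 5% | 0.75 | 1 − 0.95^15 = 54% |
| 10% | 1.5 | 1 − 0.90^15 = 79% |
| 20% | 3 | 1 − 0.80^15 = 96% |

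**5. What a Visit 1 versus Visit 6 display could show.** One event in 15 has an exact 95% interval of 0.2% to 32%. In an exact paired test, five patients with an event at one visit only, all in the same direction, give a two-sided p of 2 × 0.5^5 = 0.0625; six give 2 × 0.5^6 = 0.031. A formal comparison would therefore have little power at the rates above. The display is useful as description only.

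**The case against.** A reader might infer that Visit 1 events are simply lost, neither recorded nor reported, and that the safety result is biased against ISDN. The documents do not support that.

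- Table 1 does schedule monitoring at Visit 1. Nothing says that the Adverse Events section overrides it.
- The Adverse Events section has an IRB route for "Events that are unexpected and considered to be related or possibly related to the study procedures", and Expedited Reporting has a seven-day route for unexpected events related to study conduct. Neither has a first-dose condition.
- Events that miss the prompt-reporting criteria go to continuing review, and other SAEs and non-serious AEs go into annual reports. Unexpectedness thus governs how fast an event is reported, at least for events that have been recorded.
- Being named as a risk is not the same as being classed as expected. The Expectedness list covers headache, lightheadedness, hypotension, syncope and crescendo angina, all tied to ISDN. Arrhythmia and IV-site events are not on it, so a Visit 1 arrhythmia could qualify as unexpected and be reported promptly.
- A Visit 6 event is not automatically charged to ISDN, because the PI may grade it as unlikely related or not related. Heart rate and systemic blood pressure are also compared between the first and final visits, so some off-drug exercise information exists in any case.

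All of this stands, and it limits the point. It does not remove it. An IRB report is not an entry in the dataset from which AEs and SAEs are counted. Continuing review and annual reports can convey only what was recorded. None of these sections gives a single start date for collection or a tabulation by drug status.

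**Conclusion.** The point holds as a conflict between the Adverse Events section and Table 1, with a specific consequence if the former is followed. In that case events at the 15 planned off-drug exercise tests fall outside the AE and SAE counts, while events at the 15 on-drug tests are included. It would also be unclear whether a serious event at the Visit 1 test triggers the DSMB pause.

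The likely number of events is unknown. The 0.75, 1.5 or 3 expected at Visit 1 rest on assumed rates of 5%, 10% and 20% per test, full completion and independent patients. Counts of that order can change the impression given by an uncontrolled 15-patient safety table, though they could not separate a drug effect from an exercise effect.

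A claim that the trial has no off-drug comparator would go too far: it follows only if the first-dose rule prevails over Table 1. If Visit 1 events are collected, that test is the within-patient reference, and what is then missing is a plan to show it.

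**What to change.** 1. In Adverse Events, start recording of AEs and SAEs at informed consent or at the first study procedure, consistent with the Table 1 mark at Visit 1.
2. Reconcile the drug-based wording of the AE and SAE definitions with that start, so that it is clear how a serious event before the first dose is handled under the DSMB section.
3. In Statistical Analyses, report pre-dose events separately from on-drug events. Show exercise-test events at Visit 1 and Visit 6 side by side, descriptively and without a test.

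The cost is a short text change, slightly more adverse event recording at Visit 1 and one extra table row. No visit or procedure is added.

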#### **Serious Adverse Events**

A Serious Adverse Event (SAE) is any undesirable occurrence associated with the use of a drug in a patient occurring at any dose, whether or not considered drug related, when the outcome is:

- Death
- Life-threatening (i.e., participant was at substantial risk of dying at the time of the AE),
- Inpatient hospitalization or prolongation of existing hospitalization,
- A persistent or significant incapacity or substantial disruption of the ability to conduct normal life functions or resulted in a significant, persistent or permanent change, impairment, damage or disruption in the patient's body function/structure, physical activities and/or quality of life,
- Congenital anomaly/birth defect in the offspring of a subject who received study medication, or
- Other serious (important) medical events that may jeopardize the participant and may require medical or surgical intervention to prevent one of the other outcomes are also considered to be SAEs.

### **Relationship**

All adverse events will be classified by the PI for relationship to the study drug as: Related, Possibly Related, Unlikely Related, Not Related.

### **Severity**

All adverse events will be classified for severity by the PI as: Mild, Moderate, or Severe.

### **Expectedness**

All adverse events will be classified for expectedness by the Sponsor as: Expected or Unexpected. Expected events associated with the use of ISDN include:

- Headache
- Lightheadedness
- Hypotension
- Syncope
- Crescendo angina

### **Adverse Event Reporting:**

#### **Expedited Reporting**

SAEs require expedited reporting when meeting the following criteria:

- Serious
- Unexpected
- At least possibly related to the study drug (suspected adverse reaction)

Events that are considered unexpected and related or possibly related to the conduct of the study will be reported to the IRB within seven days of discovery.

The DSMB will review SAEs within 48 hours after initial receipt of the information by the investigator(s) to review the PIs assignment of SAE as related or unrelated to treatment; to confirm the grading of toxicity, and assure that the study may continue.

Significant unplanned deviations from the protocol will also be reported as stipulated above. All other serious adverse events and non-serious adverse events will be reported at the time of submission of annual reports. Likewise, minor deviations will be reported in annual reporting.

### **Data Safety and Monitoring:**

Data will be collected on data collection forms that will not be labeled with the patient's name, only the study number. The list of matching codes to the patient's name will be handled and retained by the study coordinator and investigator at each site. To ensure proper use and continued protection of these data, the data collection sheets will not be given to any individuals except those co-investigators and study coordinators performing data-entry.

Participant binders will be maintained with names of the subject, pertinent clinical data, and files with signed consent forms and copies of pertinent clinical and research related forms. All participant binders

and study records will be stored in locked cabinets in the PI's office or at the desk of designated research personnel. A separate Excel spreadsheet linking subject identification number to identifying information (first name, last name, medical record number, and date of birth) will also be maintained on a password-protected computer located in the PI's office or the computer of designated research personnel. Access to this information will be restricted to the PI and research staff, appropriate federal agencies, the IRB, and any sponsors of the study.

